Amended Clinical Pharmacology Study Protocol

Drug Substance Rosuvastatin Calcium
Study Code D3560C00059
Edition No. 1
Date

**A Phase I, Open Label, Parallel Group, Single and Multiple Dose Study
in Taiwanese Subjects Identified as CYP2C19 Poor Metabolizers or
Extensive Metabolizers Receiving 20 Milligrams of Rosuvastatin
Calcium**

Sponsor: AstraZeneca Taiwan, [name]

AstraZeneca Research and Development
Site Representative

The following Amendment(s) and Administrative Changes have been made to this protocol since the date of preparation:

Amendment No.	Date of Amendment
1	_____
Administrative Change No.	Date of Administrative Change
_____	_____
_____	_____

This submission /document contains trade secrets and confidential commercial information, disclosure of which is prohibited without providing advance notice to AstraZeneca and opportunity to object.

ASTRAZENECA PROCEDURES IN CASE OF EMERGENCY, OVERDOSE OR PREGNANCY

In the case of a medical emergency you may contact the Study Delivery Team Leader. If the Study Delivery Team Leader is not available, contact the Study Delivery Team Physician at the AstraZeneca Research and Development site shown below.

Role in the study	Name	Address and Telephone number
Study Delivery Team Leader		
Study Delivery Team Physician		
Product Physician		

For further clarifications regarding:

- Procedures in case of medical emergency see Section [8.2](#)
- Procedures in case of overdose see Section [8.3](#).
- Procedures in case of pregnancy see Section [8.4](#)

PROTOCOL SYNOPSIS

A Phase I, Open Label, Parallel Group, Single and Multiple Dose Study in Taiwanese Subjects Identified as CYP2C19 Poor Metabolizers or Extensive Metabolizers Receiving 20 Milligrams of Rosuvastatin Calcium

Investigator

Study center, type and number of subjects planned

This will be a single center study conducted in Taipei, Taiwan.

Approximately 25 healthy Taiwanese subjects that have been genotyped as poor metabolizers (PMs) of CYP2C19 and 25 healthy Taiwanese subjects that have been genotyped as extensive metabolizers (EMs) of CYP2C19 will be recruited to obtain at least 40 evaluable subjects (20 for each group).

An evaluable subject is defined as a subject satisfying the inclusion and exclusion criteria, completing all study procedures from the screening period to the final blood sampling for plasma levels of rosuvastatin, and had no major protocol deviation or violation.

Study period

Estimated date of first subject enrolled

Estimated date of last subject completed

Phase of development

I

Objectives

Primary Objectives

The primary objectives of this study are to:

- Explore the exposure of rosuvastatin calcium in Taiwanese subjects who have been identified as CYP2C19 PMs to exposure in Taiwanese subjects who have been identified as CYP2C19 EMs by examining the pharmacokinetic profile of rosuvastatin and its metabolites after single and multiple dosing of 20 milligrams (mg) rosuvastatin calcium

- Measure the effect of rosuvastatin calcium on lipid parameters as compared to baseline after 2 weeks of daily dosing of 20 mg rosuvastatin calcium.

Secondary Objective

The secondary objective of this study is to assess safety and tolerability.

Study design

This is an open label, parallel group, single and multiple dose study.

Investigational product, dosage and mode of administration

Rosuvastatin calcium will be administered as a 20 mg oral dose.

Duration of treatment

Approximately 25 subjects identified as PMs of CYP2C19 and 25 subjects identified as EMs of CYP2C19 (to obtain 20 subjects each) will participate for approximately 53 days including a 35-day screening period, 6 inpatient days and 12 outpatient days.

Variables

- Pharmacokinetic

The primary variables to be assessed for rosuvastatin after a single dose are:

- C_{\max} maximum plasma concentration
- AUC area under the plasma concentration-time curve from zero to infinity
- $AUC_{(0-t)}$ area under the plasma concentration-time curve from zero to time of last quantifiable concentration
- AUMC area under the first moment curve
- t_{\max} time to maximum concentration
- λ_z terminal elimination rate constant
- $t_{1/2,\lambda_z}$ half-life associated with the terminal slope (λ_z) of a semi logarithmic plasma concentration-time curve
- MRT mean residence time
- CL/F apparent oral clearance
- Vd/F apparent volume of distribution

The primary variables to be assessed for rosuvastatin after multiple dosing are:

- $C_{ss,max}$ maximum plasma concentration at steady state
- $C_{ss,min}$ minimum plasma concentration at steady state
- $C_{ss,av}$ average plasma concentration at steady state
- $t_{ss,max}$ time to maximum concentration at steady state
- $t_{ss,1/2}$ the apparent terminal half-life at steady-state
- AUC_{ss} area under the concentration-time curve at steady state
- DF degree of fluctuation (at steady state)
- AR Accumulation ratio (at steady state)

The secondary variables to be assessed for rosuvastatin metabolites N-desmethyl rosuvastatin and rosuvastatin lactone after a single dose are:

- C_{max} maximum plasma concentration
- AUC area under the plasma concentration-time curve from zero to infinity
- $AUC_{(0-t)}$ area under the plasma concentration-time curve from zero to time of last quantifiable concentration
- t_{max} time to maximum concentration
- λ_z terminal elimination rate constant
- $t_{1/2,\lambda_z}$ half-life associated with the terminal slope (λ_z) of a semi logarithmic plasma concentration-time curve

The secondary variables to be assessed for rosuvastatin metabolites N-desmethyl rosuvastatin and rosuvastatin lactone after multiple dosing are:

- $C_{ss,max}$ maximum plasma concentration at steady state
- $C_{ss,min}$ minimum plasma concentration at steady state
- $C_{ss,av}$ average plasma concentration at steady state
- $t_{ss,max}$ time to maximum concentration at steady state
- AUC_{ss} area under the concentration-time curve at steady state
- DF degree of fluctuation (at steady state)

- AR Accumulation ratio (at steady state)

Maximum concentration (C_{max}) and area under the concentration curve from zero to infinity (AUC) of rosuvastatin will be the primary variables for this study to summarize exposure in each subject. If AUC data cannot be determined in all subjects completing the study, area under the curve of plasma concentration against time from zero to last quantifiable concentration ($AUC_{(0-t)}$) will replace AUC as the primary variable.

- Pharmacodynamic

Blood samples (10 mL) will be collected for assessment of pharmacodynamic (lipid) parameters on the mornings of Days -1 and 18.

Pharmacodynamic variables will include the following:

- tChol total cholesterol
- LDL-C low-density lipoprotein cholesterol
- HDL-C high-density lipoprotein cholesterol
- TG triglycerides

- Safety

Safety and tolerability of rosuvastatin calcium will be evaluated by physical examination, clinical laboratory tests, vital signs, and collection of adverse events.

- Genetics

After signing informed consent, prospective subjects will have whole blood collected and genotyped to determine if they are PMs (CYP2C19 *2/*2, *2/*3, or *3/*3 alleles) or EMs (CYP2C19 *1/*1, *1/*2, or *1/*3 alleles) of CYP2C19.

To control for other possible genetic factors that may contribute to increased exposure of rosuvastatin, all prospective subjects coding for OATP-C 1B1 *5 and *15, and/or BCRP 421C>A will be excluded from the study. Additionally, prospective subjects must code for wild-type CYP2C9 (*1 homozygous or heterozygous). There will be no other genetic research completed on the blood samples collected.

- Statistical methods

Demographics and baseline endpoints will be analyzed using descriptive statistics (number [n], mean, standard deviation, median, minimum and maximum) for continuous variables and frequency counts and percentages for categorical variables.

Except for t_{max} , descriptive statistics will be used to summarize pharmacokinetic data for each treatment group (n, mean, standard deviation, minimum, median, maximum, geometric mean,

and coefficient of variation [CV] percentages); t_{\max} will be summarized using n, minimum, median, and maximum.

Geometric means (including 95% confidence intervals [CIs]) and CV will be calculated and listed. In addition, the geometric mean ratios, (PMs vs. EMs) of AUC, AUC_(0-t), C_{max}, (for rosuvasatin, N-desmethyl rosuvasatin, and rosuvasatin lactone) and metabolite to parent ratios and their 90% CIs will also be calculated.

Half-lives for the two groups will be summarized using least squares means and the comparison between PMs and EMs will be by least squares mean difference and 90% CI.

To evaluate whether steady state has been reached, the trough values of individual subjects will be plotted against time.

Descriptive statistics will be presented for tChol, LDL-C, HDL-C, and TG, and their changes from baseline. Baseline is defined as the lipid profile measurements before dose administration.

This study is exploratory and not powered to obtain a formal statistical comparison between PMs and EMs of CYP2C19 and exposure to rosuvasatin calcium.

	PAGE
TITLE PAGE.....	1
PROTOCOL SYNOPSIS.....	3
TABLE OF CONTENTS.....	8
LIST OF ABBREVIATIONS AND DEFINITION OF TERMS	12
1. INTRODUCTION	15
1.1 Background	15
1.2 Rationale	15
1.2.1 CYP2C19	16
2. STUDY OBJECTIVES.....	16
2.1 Primary objectives	16
2.2 Secondary objective(s).....	16
3. STUDY PLAN AND PROCEDURES	16
3.1 Overall study design	16
3.1.1 Stopping criteria for dose escalation – Not applicable	17
3.2 Rationale and risk/benefit assessment.....	20
3.2.1 Rationale for study design, doses and control groups.....	20
3.2.2 Risk/benefit and ethical assessment.....	20

Appendix A Signatures

[Appendix B](#) Additional Safety Information

[Appendix C](#) WHO Risk Categories

[Appendix D](#) Preparation of Buffer Solution for Rosuvastatin plasma samples

LIST OF ABBREVIATIONS AND DEFINITION OF TERMS

The following abbreviations and special terms are used in this study protocol.

Abbreviation or special term	Explanation
λ_z	Terminal elimination rate constant
Ad libitum	As desired
ADME	Absorption/Distribution/Metabolism/Excretion
AE	Adverse event
Assessment	An observation made on a variable involving a subjective judgment
ALT	Alanine aminotransferase
ApoB	Apolipoprotein B
AR	Accumulation ratio (at steady state)
AST	Aspartate aminotransferase
AUC	Area under the concentration curve from zero to infinity
$AUC_{(0-t)}$	Area under the curve of plasma concentration against time from zero to time of last quantifiable concentration
AUC_{ss}	Area under the concentration-time curve at steady state
AUMC	Area under the first movement curve
BMI	Body mass index
BCRP	Breast cancer resistance protein
BUN	Blood urea nitrogen
°C	Degrees Celsius
CI	Confidence interval
CK	Creatine kinase
CL/F	Apparent oral clearance
C_{last}	Last quantifiable plasma concentration after single dose or last administration
C_{max}	Maximum concentration
CRC	Clinical research center
CRF	Case report form
CSR	Clinical study report
$C_{ss,av}$	Average plasma concentration at steady state
$C_{ss,max}$	Maximum plasma concentration at steady state

Abbreviation or special term	Explanation
C _{ss,min}	Minimum plasma concentration at steady state
CV	Coefficient of variance
CYP2A6	Cytochrome P450, family 2, subfamily A, polypeptide 6
CYP2C9	Cytochrome P450, family 2, subfamily C, polypeptide 9
CYP2C19	Cytochrome P450, family 2, subfamily C, polypeptide 19
CYP2D6	Cytochrome P450, family 2, subfamily D, polypeptide 6
DF	Degree of fluctuation (at steady state)
DNA	Deoxyribonucleic acid
ECG	Electrocardiogram
EDTA	Ethylenediamine tetra-acetic acid
EM	Extensive metabolizer
G	Relative centrifugal force
GCP	Good Clinical Practice
gmean	Geometric mean
HbsAG	Hepatitis B surface antigen
HCG	Human chorionic gonadotrophin
HDL-C	High density lipoprotein cholesterol
HIV	Human immunodeficiency virus
HMG-CoA	3-hydroxy-3methylglutaryl coenzyme A
ICH	International Conference on Harmonization
Kg	kilogram
LDH	Lactic dehydrogenase
LDL	Low density lipoprotein
LDL-C	Low density lipoprotein cholesterol
LC/MS/MS	Liquid chromatography/mass spectrometry/mass spectrometry
MedDRA	Medical Dictionary for Drug Regulatory Activities
mg	Milligram
mL	Milliliter
MRT	Mean residence time
n	number

Abbreviation or special term	Explanation
OAE	Other Significant Adverse Event (i.e., adverse events of particular clinical importance, other than SAEs and those AEs leading to discontinuation of the subject from study treatment; see definition in Section 4.7.1.1)
OATP-C1B1	Organic anion transporter polypeptide solute carrier family, member 1B1
OTC	Over-the-counter
pCRF	Paper Case Report Form
PM	Poor metabolizer
PP	Per protocol
Parameter	A quantity (usually unknown) that characterizes the distribution of a variable in a population of subjects
SAE	Serious adverse event
SAP	Statistical analysis plan
τ	Dosing interval (hours)
$t_{1/2,\lambda z}$	half-life associated with the terminal slope (λ_z) of a semi logarithmic plasma concentration-time curve
tChol	Total cholesterol
TG	Triglycerides
t_{max}	Time to maximum concentration
$t_{ss,1/2}$	the apparent terminal half-life at steady-state
$t_{ss,max}$	Time to maximum concentration at steady state
ULN	Upper limit of normal
Variable	A characteristic or a property of a subject that may vary e.g., from time to time or between subjects
Vd/F	Apparent volume of distribution
VLDL	Very low density lipoproteins

1. INTRODUCTION

Rosuvastatin is a selective, potent and competitive inhibitor of HMG-CoA reductase, the rate-limiting enzyme that converts 3-hydroxy-3-methylglutaryl coenzyme A to mevalonate, a precursor of cholesterol. Triglycerides (TG) and cholesterol in the liver are incorporated, with apolipoprotein B (ApoB), into very-low-density lipo-proteins (VLDL) and released into the plasma for delivery to peripheral tissues. VLDL particles are TG-rich. Cholesterol-rich low-density-lipoprotein (LDL) is formed from VLDL and is cleared primarily through the high affinity LDL receptor in the liver.

Rosuvastatin produces its lipid-modifying effects in two ways; it increases the number of hepatic LDL receptors on the cell-surface, enhancing uptake and catabolism of LDL and it inhibits the hepatic synthesis of VLDL, thereby reducing the total number of VLDL and LDL particles.

Rosuvastatin undergoes first pass extraction in the liver, which is the primary site of cholesterol synthesis and low-density lipoprotein cholesterol (LDL-C) clearance.

Rosuvastatin is not extensively metabolized; approximately 10% of a radiolabeled dose is recovered as metabolite. The major metabolite is N-desmethyl rosuvastatin, which is formed principally by cytochrome P450 2C9.

In vitro and in vivo data indicate that rosuvastatin clearance is not dependent on metabolism by cytochromes P450 3A4 and 2C9 to a clinically significant extent. Rosuvastatin also does not interact to a clinically significant extent with the p-glycoprotein transporter.

1.1 Background

Previous studies have demonstrated that for the same dose of rosuvastatin, systemic exposure in Japanese subjects living in Japan is approximately two-fold higher than the exposure observed in Caucasian subjects living in Europe. The results of a study in subjects in Singapore found that rosuvastatin plasma exposure in Chinese, Malay, and Indian subjects was approximately 2-fold higher compared to a Caucasian control group living in Singapore. In a United States study comparing plasma exposure in 6 different Asian ethnic groups (Chinese, Filipino, Asian Indian, Korean, Vietnamese, and Japanese) living in the United States to a Caucasian control group, plasma exposure was consistently higher across the Asian ethnic groups, with the exception of the Asian Indian group which was intermediate.

1.2 Rationale

In Asians, approximately 20% of the population can be identified as poor metabolizers (PMs) of CYP2C19. Although CYP2C19 has not been identified as the primary metabolic pathway in the metabolism of rosuvastatin calcium, it has been established that it does play some role. Because it has been established that Asians inherently have a higher exposure to rosuvastatin, it is important to compare the exposure in Asians identified as PMs of CYP2C19 to those

identified as extensive metabolizers (EMs) to determine if there are further significant differences in exposure between these groups.

The pharmacodynamic effect of rosuvastatin calcium in Taiwanese subjects is included in this study as part of the continued licensing requirements of rosuvastatin calcium in Taiwan.

1.2.1 CYP2C19

In the P450 cytochrome enzyme family, CYP2D6, CYP2C9, CYP2C19 and CYP2A6 are functionally polymorphic. Together these isoenzymes represent approximately 40% of human P450 dependent drug metabolism, and therefore are significant due to the wide variations possible in mutated alleles. Currently there are 12 different alleles of the CYP2C19 gene that have been identified. Eleven of these alleles code for inactive versions of the enzyme. These mutated alleles are identified as CYP2C19 *2, *2B to *11. The nomenclature for the wild-type allele is CYP2C19*1. Individuals are considered EMs if at least one wild-type allele is present. Individuals are considered PMs if both alleles code for inactive enzymes. In Asians, the alleles CYP2C19*2 and *3 together account for the majority of defective alleles in PMs.

2. STUDY OBJECTIVES

2.1 Primary objectives

The primary objectives of this study are to:

- Explore the exposure of rosuvastatin calcium in Taiwanese subjects who have been identified as CYP2C19 PMs to exposure in Taiwanese subjects who have been identified as CYP2C19 EMs by examining the pharmacokinetic profile of rosuvastatin and its metabolites after single and multiple dosing of 20 milligrams (mg) rosuvastatin calcium
- Measure the effect of rosuvastatin calcium on lipid parameters of Taiwanese subjects after 2 weeks of daily dosing of 20 mg rosuvastatin calcium

2.2 Secondary objective(s)

The secondary objective of the study is to assess safety and tolerability

3. STUDY PLAN AND PROCEDURES

3.1 Overall study design

This Clinical Study Protocol has been subjected to a peer review according to AstraZeneca standard procedures.

This is an open label, parallel group, single and multiple dose study.

After signing informed consent, prospective subjects will have approximately 9 mL of whole blood collected for genotyping. Approximately 20-25 poor metabolizers of CYP2C19 (CYP2C19 *2/*2, *2/*3, or *3/*3 alleles) and 20-25 EMs of CYP2C19 (CYP2C19 *1/*1, *1/*2, or *1/*3 alleles) will be randomly selected to continue with the study.

To control for other possible genetic factors that may contribute to increased exposure of rosuvastatin, all prospective subjects coding for OATP-C 1B1 *5 and *15, and/or BCRP 421C>A will be excluded from the study. Additionally, prospective subjects must code for wild-type CYP2C9 (*1 homozygous or heterozygous). There will be no other genetic research completed on the blood samples collected.

The study period will start with a screening visit. Subjects will undergo a health examination including physical examination, ECG, vital signs, clinical laboratory tests, and urinalysis.

Subjects will be admitted to the clinical research center (CRC) on Day -1. Day -1 assessments will be completed and blood will be collected for a pre-treatment (baseline) lipid profile. After an overnight fast, subjects will receive a 20 mg rosuvastatin calcium tablet on Day 1. Blood samples will be collected to 72 hours post-dose to assess the pharmacokinetic profile. On the morning of Day 4, (after the 72 hour blood collection) the subjects will again be dosed with 20 mg of rosuvastatin. The subjects will then be discharged from the CRC with study drug and instructions to take one 20 mg tablet of rosuvastatin calcium each morning for the next 2 days (Days 5-6). On the mornings of Days 7, 8, and 9 the subjects will return to the CRC to have blood collected for trough levels of rosuvastatin prior to dosing. After blood collection and dosing on Day 9, the subjects will leave the CRC with study drug and instructions to take one 20 mg tablet of rosuvastatin calcium each morning for the next 7 days (Days 10-16). The subjects will return to the CRC in the afternoon of Day 16 for readmission to the CRC. On the morning of Day 17, subjects will receive the last dose of 20 mg rosuvastatin calcium and blood samples will be collected to 24 hours post dose to assess the pharmacokinetic profile at steady-state. On Day 18, final assessments, including a blood sample to assess post-treatment lipid profiles, will be completed and the subjects discharged from the study.

3.1.1 Stopping criteria for dose escalation – Not applicable

Figure 1 Study flow chart

[figure not shown]

Table 1 Study plan

Study Procedures	Pre-Screening	Screening	Day -1	Days 1-4	Days 5-6	Day 7-9	Days 10-15	Day 16	Day 17	Day 18
Informed Consent	X									
Inclusion/Exclusion Criteria	X	X	X							
Blood sample for genotyping	X									
Demographic Data		X								
Med/Medication/Surg History		X								
Urine Drug Screen		X	X							
HIV/Hepatitis Screening		X								
Serum Pregnancy Test		X	X							X
Height and Weight		X								
Body Temperature		X	X							
12-lead ECG		X								X
Urinalysis		X	X							X
Clinical Chemistry/Hematology		X	X							X
Complete Physical Examination		X								X
Brief Physical Examination			X							
Lipid Profile			X							X
Blood Pressure and Pulse		X	X	X		X			X	X
Administration of 20 mg rosuvastatin calcium				X ^a	X ^b	X ^c	X ^b	X ^b	X ^d	
Blood sampling for PK assessment of rosuvastatin calcium				X ^e		X ^f			X ^e	X
Adverse Events		X ^g	X	X	X	X	X	X	X	X
Concomitant Medications		X	X	X	X	X	X	X	X	X
In-Patient			X	X				X	X	
Out-Patient		X			X	X	X			
Discharge from study										X

- a. Rosuvastatin calcium administered on Day 1 and Day 4 only. Day 1: 20 mg rosuvastatin calcium administered by study site staff. Day 4: 20 mg rosuvastatin calcium administered by study staff after collection of 72-hour blood sample.

- b. 20 mg rosuvastatin calcium self administered by subjects while out-patient
- c. 20 mg rosuvastatin calcium administered by study site staff after collection of blood samples for trough levels
- d. 20 mg rosuvastatin administered by study site staff
- e. Serial blood sampling for rosuvastatin will be done at the following time points: Day 1 pre-dose (within 30 minutes), and 0.5, 1, 2, 3, 4, 5, 6, 8, 10, 12, 18, 24, 30, 36, 48, 54, 60, and 72 hours post-dose; Day 17 pre-dose (within 30 minutes), and 0.5, 1, 2, 3, 4, 5, 6, 8, 10, 12, 18, and 24 hours post-dose
- f. Pre-dose blood samples collected for trough levels
- g. Adverse events (AEs) will be collected beginning Day -1 through final assessment on Day 18. Serious adverse events (SAEs) will be collected from the time the informed consent is signed through final assessments on Day 18

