4.6 Volume of blood sampling

The total volume of blood that will be drawn from each subject in this study is as follows:

Table 4 Volume of blood to be drawn from each subject

Assessment	Sample volume (mL)	n of samples	Total volume (mL)
Blood sampling for rosuvastain	4 mL	35	140 mL
Genetic sample	9 mL	1	9 mL
Lipid profile	10 mL	2	20 mL
Safety HIV/HbsAG/ Hep C	10 mL	1	10 mL
Clinical chemistry	10 mL	3	30 mL
Hematology	10 mL	3	30 mL
Total		45	239 mL

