4.7.1 Adverse Events

4.7.1.1 Definitions

The definitions of adverse events (AEs), serious adverse events (SAEs) and other significant adverse events (OAEs) are given below. It is of the utmost importance that all staff involved in the study is familiar with the content of this section. The principal investigator is responsible for ensuring this.

Adverse event

An AE is the development of an undesirable medical condition or the deterioration of a pre-existing medical condition following or during exposure to a pharmaceutical product, whether or not considered causally related to the product. An undesirable medical condition can be symptoms (eg, nausea, chest pain), signs (eg, tachycardia, enlarged liver) or the abnormal results of an investigation (e.g., laboratory findings, electrocardiogram). In clinical studies, an AE can include an undesirable medical condition occurring at any time, including run-in or washout periods, even if no study treatment has been administered.

Serious adverse event

A SAE is an AE occurring during any study phase (i.e., run-in, treatment, washout, follow-up), and at any dose of the investigational product, comparator or placebo, that fulfills one or more of the following criteria:

- Results in death
- Is immediately life-threatening
- Requires in-patient hospitalization or prolongation of existing hospitalization
- Results in persistent or significant disability or incapacity
- Is a congenital abnormality or birth defect
- Is an important medical event that may jeopardize the subject or may require medical intervention to prevent one of the outcomes listed above.

The causality of SAEs (ie, their relationship to study treatment) will be assessed by the investigator(s), who, in completing the relevant case report form, must answer “yes” or “no” to the question “Do you consider that there is a reasonable possibility that the event may have been caused by any of the following – study medication – other medication?”. For further guidance on the definition of a SAE and a guide to the interpretation of the causality question, see [Appendix B](#) to the Clinical Pharmacology Study Protocol.

Note that SAEs that could be associated with any study procedure should also be reported. For such events the causal relationship is implied as “yes”.

Other Significant Adverse Events (OAE)

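### Adverse event and SAE collection closes on Day 18, about 24 h after the last dose and on the day of the only post-dose safety laboratory sample, with no later contact for completers

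*Protocol*

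**What the plan says.** Footnote g of Table 1 sets two windows with the same end. For adverse events: "Adverse events (AEs) will be collected beginning Day -1 through final assessment on Day 18". For serious events: "Serious adverse events (SAEs) will be collected from the time the informed consent is signed through final assessments on Day 18".

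Section 3.1 places the end of dosing one day earlier: "On the morning of Day 17, subjects will receive the last dose of 20 mg rosuvastatin calcium and blood samples will be collected to 24" (the unit is hours after that dose). It then closes the study for the subject: "On Day 18, final assessments, including a blood sample to assess post-treatment lipid profiles, will be completed and the subjects discharged from the study". Neither section 3.1 nor Table 1 contains a visit or call after that.

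Table 1 marks the row "Clinical Chemistry/Hematology" at Screening, Day -1 and Day 18 only, and urinalysis on the same three occasions. Section 4.4.1.2 includes CK, AST and ALT in the chemistry panel.

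Section 4.7.1.1 brings test results into the definition of an adverse event: "An undesirable medical condition can be symptoms (eg, nausea, chest pain), signs (eg, tachycardia, enlarged liver) or the abnormal results of an investigation", with laboratory findings among its examples. Section 4.7.1.2 requires a start date, stop date, maximum intensity, action taken, outcome and causality for each event. The general instruction to follow up adverse events appears in section 3.3.5.2, which concerns subjects who discontinue.

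**The concern.** The protocol asks for more about each adverse event than its schedule lets the site collect from a completer. An event that begins after discharge is outside the window whether or not it is serious. An event that is open at discharge, or that becomes apparent only when the Day 18 results are read, falls inside the window, but no contact is planned at which its course can be established.

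A subject who withdraws early has a written rule for following adverse events. A subject who takes all 15 doses has none.

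Assessing safety and tolerability is the only secondary objective (section 2.2), and the subjects are healthy volunteers who gain no health benefit (section 3.2.2). Closing collection early can only lower the event count or leave event records incomplete.

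**Working it through.** No sample size or power figure is involved. The check is a count from the schedule, followed by a comparison of sections.

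**The plan's own figure.** Table 4 gives "Clinical chemistry 10 mL 3 30 mL", that is, 3 chemistry samples per subject, and also 3 for hematology. From Table 1: Screening (1) + Day -1 (1) + Day 18 (1) = 3. The figure is reproduced. Dosing starts on Day 1, so exactly 1 of the 3 is post-dose.

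**Doses before that sample.** Sections 3.1 and 3.4.2 give one dose on Day 1 and one on each of Days 4 to 17. That is 1 + (17 - 4 + 1) = 1 + 14 = 15 doses.

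**Time from first dose to that sample.** 18 - 1 = 17 days.

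**Time from last dose to the end of collection.** The last dose is on the morning of Day 17, and the final pharmacokinetic sample is 24 h later on Day 18 (Table 3). Final assessments and discharge are also on Day 18. Collection therefore runs for about 24 h after the last dose, and no day of collection follows the laboratory sample.

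**Follow-up provisions for a subject who completes.**
- Section 3.3.5.2 instructs that adverse events be followed, but its scope is discontinuation.
- Section 4.7.1.3 requires follow-up information on SAEs, and reporting when a non-serious event becomes serious. It sets no period after Day 18. A new SAE after discharge is outside footnote g.
- Section 8.4 follows pregnancy outcomes only.
- Section 4.4.1.1 allows further investigation, at the investigator's discretion, of urine positive for protein or blood.
- Section 4.7.1.1 names follow-up among the study phases in which an SAE may occur, but Table 1 has no such phase.

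None of these gives a completer a planned contact through which a stop date or outcome could be obtained for a non-serious event open on Day 18.

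**What happens to the Day 18 laboratory values.** Section 6.2 makes laboratory parameters part of the safety assessment in their own right. Section 6.2.1.1 lists every value, notes those outside the normal range, and summarizes absolute values and change from baseline. Section 4.7.1.1 allows marked laboratory abnormalities to be classed as other significant adverse events when the study report is prepared. The values are therefore reported. A listing does not carry the intensity, causality, stop date and outcome of an adverse event record.

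**The case against.** The strongest reply is that little is lost. Day 18 laboratory data are reported regardless of the adverse event form. An abnormality in blood drawn on Day 18 dates to Day 18, inside the window. Section 4.7.1.2 already requires an outcome for each event. Adverse events are collected throughout Day -1 to Day 18, and an ECG and complete physical examination are done at discharge. Safety is a secondary objective assessed descriptively, the dose is approved in Taiwan (section 3.2.1), and the protocol rates the risk of participating as low.

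Most of this stands, and it limits the point. A reader might infer that the safety objective cannot capture what the Day 18 sample shows. The documents do not support that, for the reasons in sections 6.2 and 6.2.1.1. Nor do they show that results arrive after discharge, since no laboratory turnaround time is given. The Day -1 pregnancy test, which may share the chemistry tube and can bar a subject from proceeding to dosing on Day 1, suggests that turnaround can be quick.

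Two other stronger readings also fail. The 72 h of sampling after the first dose might be taken as the period that the protocol considers relevant for safety. Section 3.1 gives its purpose as the pharmacokinetic profile, and no section uses it as a safety window. One might also want to calculate how much drug remains when collection stops. The protocol gives no half-life, the half-life it defines describes only the terminal slope and not the decline from the peak, and nothing in it links residual concentration to event risk.

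The reply does not reach two gaps. Requiring an outcome does not provide a contact at which to obtain it. And no provision makes events that start after discharge collectable.

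**Conclusion.** The point holds in a limited form. Both windows close about 24 h after the last of 15 doses, on the day of the single post-dose safety laboratory sample, and completers have no later contact. Three consequences follow:
- adverse events and SAEs that start after discharge are not collected;
- events open on Day 18 may be left without a stop date or a final outcome;
- the protocol does not say whether a Day 18 result returned after discharge is still entered as an adverse event.

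Any error runs towards fewer or less complete events. The window is the same for poor and extensive metabolizers, so no bias in the comparison between the groups is shown. The number of events affected cannot be estimated, because the protocol gives no event rates. The effect is limited to the secondary, descriptive safety objective; the pharmacokinetic and lipid analyses are untouched. No stated figure is wrong. This is an inexpensive improvement to a stated collection rule, and worth making.

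The conclusion assumes only that Table 1 and section 3.1 describe all planned contacts.

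**What to change.** Amend footnote g of Table 1, section 3.1 and section 4.7 together:
- Continue adverse event and SAE collection for a stated period after the last dose, and at least until the investigator has reviewed the Day 18 safety results. The sponsor should set and justify the length.
- Close the window with one telephone contact per subject and show it in Table 1.
- State that abnormal Day 18 results meeting the adverse event definition are recorded as adverse events even if returned after discharge.
- State that events open on Day 18 in completers are followed for outcome, so that the follow-up rule no longer covers discontinuers alone.

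The cost is about 50 telephone contacts (25 + 25 planned subjects) and a short delay in closing each subject. Dosing, existing visits and pharmacokinetic sampling do not change.
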